Study Protocol and Statistical Analysis Plan

Official Title: Effects of Exercise and Cognitive Training on Executive Function in Parkinson's Disease (NCT 01156714)

Document Date: 9/28/18 (date when document was most recently updated)

Study Protocol:

Screening Methods:

Screening for participation in the study will be held in 1) Baltimore VAMC, and 2) UMPDC. Patients will go through initial evaluation (history, medical & neurological exams), mental exam, visual acuity exam, exercise fitness test and daily living questionnaire. Assessment will be done during the “ON period”, when antiparkinsonian medications are working optimally. Below is a description of each assessment tool:

Informed Consent: Written consent for participation will be obtained from each participant at their first evaluation by trained study staff. Participants will undergo an Evaluation to Sign Consent. An assessment of patient understanding of the protocol is also required prior to study entry.

Hoehn & Yahr: The Hoehn & Yahr scale (57) will be used to assess general staging of PD. Classification ranges from 1 to 5, with higher scores indicating greater disability. The cut-point in the present study is stages 1- 3 (1 = Unilateral involvement only, usually with minimal or no functional impairment, 2 = Bilateral or midline involvement, without impairment of balance, 3= First sign of impaired righting reflexes; patients are physically capable of leading independent lives, and their disability is mild to moderate). This assessment will be performed by a movement disorders specialist.

UPDRS: The Motor subscale of the UPDRS (58) will be used to assess disease severity, with particular attention to items #28 (gait) and #30 (postural instability). To be included in this study, a subject must score between 1 and 3 on item #28, and 1 and 2 on item #30, indicating the some impairment of gait or balance but preserved ability to walk independently. On the motor UPDRS, scores each item ranges from 0-4 with a maximum of 108. Higher scores indicate greater disease severity. The motor UPDRS will be assessed by neurologists who specialize in movement disorders.

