TAEX Protocol: The exercise protocol of the TAEX group has been successfully implemented in patients with PD. Subjects will exercise 3 times per week for 3 months. Treadmill walking will start conservatively at 15 minutes with target heart rate 40–50% of maximal heart rate reserve (HRR), by the formula of Karvonen (64). Subjects incapable of continuous treadmill walking will perform intermittent exercise until 20 minutes is achieved. Exercise intensity and duration will be increased by 5 minutes every two weeks, and 0.1 MPH increments as tolerated until reaching a target of 30 minutes at 70-80% HRR. Speed and/or hill will be increased as tolerated every week to maintain the 70-80% HRR. Vital signs will be taken prior, during and after exercise. Heart rate monitoring (Polar) will be used to monitor exercise intensity. Training will

be discontinued for blood pressure drop > 20 mm Hg for medical evaluation. Logbooks will be used to document daily training parameters, complaints or concerns. All participants will be supported in a non-weight bearing fashion in a Biodex™ harness (Biodex Medical Systems, Inc Shirley, NY) to eliminate risk of falls. Health professionals credentialed in exercise training and cardiopulmonary resuscitation will monitor all training sessions at each intervention site (Baltimore VAMC and Parkinson & Movement Disorder Center).

TCOG Protocol: Subjects in the TCOG group will perform cognitive training 3 times per week for 3 months. A commercially available computer-based program will be used (Insight Program by Posit Science, San Francisco, CA). This program was chosen for our study because it has been validated in studies of older adults (14, 15) and is readily available for use. Training will consist of five visual-based exercises designed to improve divided attention, working memory, visual information processing speed, and useful field of view. The program is set up so that the level of difficulty is continuously adjusted to user performance, to maintain a correct rate of about 85%. The program uses a Bayesian algorithm to estimate and then adjust to the individual's performance on a trial-by-trial basis (66). Correct trials are rewarded with points and animations.

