d. Over-ground Gait Economy: Over-ground gait economy will be measured using a portable metabolic monitoring system, K4b2 (Cosmed; Rome, Italy) during a 6 minute walk, with subjects walking at their comfortable self-selected walking speed while open circuit spirometry collects break-by-break data. The K4b2 consists of a small battery pack and portable gas analyzer (weighing less than 1 kg) that participants wear on their chest. Attached to the portable system is a flexible rubber facemask with flowmeter used for breath-by-breath analysis. The mean rate of VO_2 will be calculated based on the final 3 minutes of a 6-minute walk under steady state oxygen consumption conditions. A 6 minute walk is a distance most representative of community-based ambulatory capacity and is a sensitive outcome measure in exercise studies in chronic stroke subjects. Prior to performing the 6 minute walk, subjects will undergo a period of acclimatization so subjects can feel comfortable wearing the rubber facemask described above. Following this familiarization period, subjects will be seated for a 10 minute rest period prior to performing the 6 minute walk. Subjects will use the same assistive device and/or orthoses typically used and will be instructed to cover as much distance as they can over a flat 100-foot walking surface demarcated by traffic cones.

Behavioral Measures:

Psychiatric and behavioral features may interfere with cognitive performance (76, 77). We will control for the potential confounding effects of depression, apathy, fatigue, and self-efficacy on cognitive performance of our patients by assessing the following measures:

a. Beck Depression Inventory:

Depression will be assessed with the Beck Depression Inventory (BDI) (78). This measure has been shown to be valid for screening and diagnosis of depression in patients with PD (79). The BDI is a self-rating questionnaire that consists of 21 statements describing how you feel over the past week. The highest score on each item is 3 and for the full test (63), indicating extreme depression.

b. Apathy Evaluation Scale:

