Washington) will be used to assess home ambulatory function. Previous research by our group has validated this device for patients with PD and has shown that step count as measured by this device is highly correlated with disease severity in PD (85). Subjects will wear the SAM at home over 48 hours while performing their usual daily routines (removing it during bathing and sleep). Recording will be done on the days that immediately precede or follow the on-site clinical testing of the other outcome measures. Placement of the SAM will be taught to the subject on site during their first testing session. Individual calibration will be done based on each subject's height and gait (e.g. subjects will perform a 30-foot walk while an examiner records time and number of steps without the SAM). Two variables will be measured: mean step count per day and maximal number of steps per hour.

Statistical Analysis Plan (SAP):

The data from the study will be entered into a dataset and validated by the investigators. Descriptive statistics will be calculated for all variables using SAS version 9.1 (SAS institute, Cary, N.C.). Exploratory data analyzes will be performed to check the data for extreme values and to test for normality (Kolmogorov-Smirnov test). If our data is not normally distributed, we will try conventional normalizing and/or variance stabilizing transformations to obtain something close enough to a Gaussian distribution to enable the use of parametric statistics. A two-tailed $p < 0.05$ will be considered indicative of a significant result. Below is a description of the statistical analyses to test each hypothesis of this study:

Hypothesis I: The combined intervention TAEX + TCOG group will show greater improvement in EF than either group alone.

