EF performance will be stratified into domains and standardized as composite scores using z-score transformation. In addition, an overall composite variable will be derived from the ANAM battery, representing an Index of Cognitive Efficiency (ICE). The ICE will be derived by weighting throughput scores from the individual ANAM tests and then combining them into a single score reflecting overall performance on the test battery. The weighting will be done so that each score contributes equally to the overall index with higher scores indicative of better test performance. This method has been used in previous studies to combine data in an efficient manner to look at cognitive performance over time (86). Our dependent variables are: 1) a total z-score for each EF domain and 2) the ICE.

Each dependent variable will be evaluated with a parametric Mixed Models Repeated Measures Analysis of Variance (ANOVA), with Group as the between factor (TAEX, TCOG, TAEX+TCOG) and Time as the within factor (pre-test, post-test). Therefore, each intervention group will be compared against each other, and against the baseline phase (i.e. those undergoing delayed entry). We will adjust for potential confounding variables such as age, educational level, and behavioral variables (depression, fatigue, apathy and self-efficacy) by including these in the analysis as covariates. Post-hoc pair-wise comparisons will be done using Tukey's Honestly Significant Difference with an $\alpha = 0.05$ as the experiment-wise error rate. An intention-to-treat analysis paradigm will be used to account for missing data (e.g. subjects from whom we have obtained data at baseline, but who later drop out). The data collected from these subjects along with those who completed the study will be combined using multiple imputation. These analyses will be performed using the SAS procedures PROC MI and PROC MIANALYZE and

will provide insight into the effectiveness of our interventions.

Hypothesis II: The combined intervention TAEX + TCOG group will show greater improvement in DT than either group alone.

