Our dependent variables on DT performance are: 1) the number of words generated per second, 2) spatiotemporal gait parameters including walking speed, stride length, cycle time, and variability of cycle time, 3) Cognitive Cost and 4) Gait Cost. Each dependent variable will be evaluated with a parametric Mixed Models Repeated Measures Analysis of Variance (ANOVA), with Group as the between factor (TAEX, TCOG, TAEX+TCOG) and Time as the within factor (pre-test, post-test). Therefore, each intervention group will be compared against each other, and against the delayed entry phase. Similar to the analysis described under Hypothesis I, we will adjust for potential confounding variables, run a Tukey's Honestly Significant Difference post-hoc test, and perform an intention-to-treat analysis for Hypothesis II.

Hypothesis III: Improvement in DT performance will be associated with improvement in IADLs function.

Our IADL measures are: 1) OARS IADLs, 2) Timed IADLs and 3) daily activity as measured by the SAM. To test Hypothesis III, these measures will be converted into change scores. Therefore our dependent measures are: 1) OARS change scores (post-test – pretest), 2) Timed IADLs (post-test – pretest), 3) SAM change scores (post-test – pretest). These measures will be correlated with DT performance measures, also represented as change scores.

Correlations between OARS IADLs change scores and DT change scores will be calculated using non-parametric statistics, Spearman Correlation Analysis, because OARS produces rank-ordered data. Correlations between Timed IADLs change and DT change, as well as correlations between SAM change and DT change will be calculated using parametric statistics: Pearson Product Moment Correlation Analysis.

Secondary analyses:

In order to investigate whether EF improvements are associated with cardiopulmonary fitness improvements, we will run Pearson Product Moment Correlations. Correlated variables will be: 1) change in EF performance (z-scores and ICE) where change is calculated as pre-test – post-test, and 2) change in cardiopulmonary fitness measures (Peak VO₂ max, METs, 6 min walk test time) where change is calculated as pre-test – post-test.

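### Hypothesis II borrows an open covariate list with no motor measure for mostly gait outcomes; a pre-specified post-test model with pre-test and motor UPDRS would be a cheap improvement

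*Combined protocol and SAP*

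**What the plan says.** Under Hypothesis I the SAP states: "We will adjust for potential confounding variables such as age, educational level, and behavioral variables (depression, fatigue, apathy and self-efficacy". The list is introduced as examples, so it is not closed. Hypothesis II adds nothing specific: "Similar to the analysis described under Hypothesis I, we will adjust for potential confounding variables".

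The Behavioral Measures section gives the reason for the four behavioural scores: "We will control for the potential confounding effects of depression, apathy, fatigue, and self-efficacy on cognitive performance of our patients".

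Hypothesis II has seven outcomes. Five concern gait: walking speed, stride length, cycle time, cycle-time variability and Gait Cost. The other two are words per second and Cognitive Cost. Each is analysed by a repeated-measures mixed model with Group and Time factors, pre-test and post-test both being outcomes. The hypothesis is about improvement.

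Under Screening Methods, "The Motor subscale of the UPDRS (58) will be used to assess disease severity", rated by movement-disorder neurologists. Neither this score nor Hoehn & Yahr stage appears anywhere in the SAP. In the Activity Monitor section the protocol reports that "step count as measured by this device is highly correlated with disease severity in PD".

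**The concern.** A list justified largely by its effect on cognition is carried over to outcomes that are mostly about walking. A motor severity score is available at no extra cost, and the investigators themselves tie severity to ambulation, yet the plan does not name it. Because the list is open, the choice could also be made after the data are seen.

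At stake is the precision of the combined-versus-single contrasts on gait and dual-task outcomes, and whether the adjustment is fixed in advance. How much precision depends on how the covariate enters the model, so that has to be settled first.

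**Working it through.** **Inputs.** The model, outcomes and covariates are those in the SAP. The documents give no sample size, SD, correlation or allocation method, so there is no stated figure to reproduce. Assumed: n = 15 to 30 per arm in three arms (N = 3n); pre-post correlation ρ = 0.6 to 0.8; correlation of severity with the outcome at each visit s = 0.3 to 0.5; severity unrelated to change; the six named covariates uninformative.

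**Step 1: UPDRS as a main effect.** A covariate with one value per patient adds the same amount to both visits, so it drops out of post minus pre. In one simulated data set (20 per arm, s = 0.5, ρ = 0.7) the two Group by Time estimates were -0.0421 and -0.3843, each with SE 0.2226, with or without a UPDRS main effect. A UPDRS-by-Time term gave SEs of 0.2246 and 0.2254, slightly worse, because severity was generated unrelated to change.

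**Step 2: if severity does predict change.** With correlation r between severity and change, a UPDRS-by-Time term multiplies the SE by √(1 - r²): 0.980, 0.954 and 0.917 for r = 0.2, 0.3 and 0.4. Power of 80% becomes 81.6, 83.6 and 86.4% (one pairwise contrast, no Tukey correction). At r = 0 nothing is gained.

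Chance imbalance is not a second loss. Under randomisation the difference in mean severity between two arms has SD √(2/n), so it typically moves the contrast by r√(2/n) in SDs of change. The contrast's own SE is √(2/n) in the same units. The shift is therefore r times the SE, which is the r² share of variance (4 to 16%) already counted.

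**Step 3: post-test model with pre-test and UPDRS.**

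- Pre-test: the variance of change is 2(1 - ρ); the variance of post given pre is 1 - ρ². SE ratio A = √((1 + ρ)/2), which is 0.894 at ρ = 0.6 and 0.949 at ρ = 0.8.
- UPDRS: its partial correlation with post given pre is p = s(1 - ρ)/√((1 - s²)(1 - ρ²)). SE ratio B = √(1 - p²).
- Cost of estimating q covariates: the contrast variance is multiplied by F(q) = 1 + q/(N - q - 4). For N = 45, F(6), F(7) and F(8) are 1.171, 1.206 and 1.242. For N = 90 they are 1.075, 1.089 and 1.103.

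The two ends of the range, with the six named covariates acting on the contrast in both models:

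| | Least favourable | Most favourable |
|---|---|---|
| n, ρ, s | 15, 0.8, 0.3 | 30, 0.6, 0.5 |
| p | 0.06/0.572 = 0.105 | 0.20/0.693 = 0.289 |
| B | 0.9945 | 0.957 |
| Total: A × B × √(F(8)/F(6)) | 0.949 × 0.9945 × 1.030 = 0.972 | 0.894 × 0.957 × 1.013 = 0.867 |
| Pre-test alone: A × √(F(7)/F(6)) | 0.963 | 0.900 |
| UPDRS alone: B × √(F(8)/F(7)) | 1.009 | 0.964 |

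The total gain is thus about 3 to 13%: 4 to 10% from the pre-test, and between a 1% loss and a 4% gain from UPDRS. If UPDRS were wholly uninformative (s = 0), its cost would be √(F(8)/F(7)) = 1.015 at 15 per arm and 1.006 at 30. Simulation of these models agreed with the formulas to within about 0.02.

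**Step 4: the basis of comparison.** Leaving the six covariates out of both models gives the same range: 0.949 × 0.9945 × √1.051 = 0.967 to 0.894 × 0.957 × √1.024 = 0.866. But if the planned model carries them only as main effects, they do not touch its contrast (Step 1), whereas in a post-test model they do. The ratio then runs from 0.949 × 0.9945 × √1.242 = 1.052 to 0.894 × 0.957 × √1.103 = 0.899, that is, from a 5% loss to a 10% gain if none of the six is informative.

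**The case against.** The case against is strong on several counts, and most of it stands.

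- The list is open, so UPDRS is not excluded. That stands: the fair criticism is that the covariates are not pre-specified.
- The borrowed covariates are not misplaced. Two of the seven outcomes, words per second and Cognitive Cost, have a cognitive content. That stands, and nothing here removes them.
- A reader might infer that leaving out severity makes the gait contrasts noisier and more open to chance imbalance. The documents do not support this. Stable severity cancels from the planned contrast. The step-count statement concerns a level rather than a change, and home step count is a Hypothesis III measure. No section links severity to training response. Entry limits on Hoehn & Yahr stage and UPDRS items 28 and 30 also restrict the range of severity. Chance imbalance presumes random allocation, which these documents do not describe.
- A reader might also infer that training site is a missing covariate, since the TAEX Protocol refers to "each intervention site (Baltimore VAMC and Parkinson & Movement Disorder Center". Nothing states that site is a recorded field, and Outcomes Testing places all pre-tests and post-tests at the Baltimore VAMC. Only differences in delivery could remain.

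On the other side, the TAEX Protocol advances speed as tolerated and lets those unable to walk continuously start intermittently, so a link between severity and response is plausible. It is not quantified.

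**Conclusion.** The point holds as a modest, low-cost improvement to the plan; it is not an error. Hypothesis II has no covariate list of its own, the borrowed list is open and names no motor measure, and a suitable motor score is already collected.

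Under the stated assumptions, and with the named covariates handled alike in both models, the proposed model cuts the contrast's standard error by about 3 to 13%. The pre-test adjustment does most of this, and UPDRS contributes little either way. The true gain cannot be derived from the documents. With small arms it could vanish if the six named covariates are uninformative and the present plan carries them only as main effects. A loss of precision or robustness from omitting severity in the planned model is conditional on severity predicting change.

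**What to change.** In the Hypothesis II section, replace the cross-reference with a closed specification. For each gait and dual-task outcome, model the post-test value on Group, that outcome's own pre-test value, the screening motor UPDRS score, and the covariates already named at their pre-test values. Remove the open wording. Do not simply append UPDRS as a main effect to the Group by Time model. Include a site term only if patients trained at both sites and site is recorded.

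The cost is a few lines of SAP text and no new data. Pre-test and UPDRS use two degrees of freedom, one each. An uninformative UPDRS would cost about 0.6% of precision at 30 per arm and 1 to 1.5% at 15. If the arms are near the small end, the sponsor should confirm that all six named covariates are worth keeping before fixing the list.

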2) Single task gait- subjects will walk 50 feet at a comfortable speed, on the 24 foot Gaitrite mat, turning twice to complete 50 feet total

3) Dual task- generating words that start with letter “f” while walking 50 feet on Gaitrite, subjects will be tape recorded during task performance so that rate of word production relative to walking speed can be analyzed. Start of tape recorder will be synched to start of walking.

Walking spatial-temporal parameters will be measured using the Gaitrite 24 foot gait mat with existing hardware and software for analysis.

Outcome Measures specific to Aim 3: Investigate whether improvement in DT performance translates into improved function in IADLs.

Daily activity Measures:

a. OARS:

A detailed description of the OARS was provided in section 1.4.4. Validity and reliability for the OARS has been reported in the geriatric population (83). As described previously, the OARS is composed of ADL and IADL. Higher scores represent greater disability. For the purposes of this study (Aim III), we will focus our analysis on the IADL component of the scale. One limitation of this scale is that there may be a floor effect, due to the categorical nature of the scale (see preliminary data section f). This limitation is addressed by adding a second IADL measure: the Timed IADL test.

b. Timed IADLs:

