Reliability and validity of Timed IADLs has been reported in older adults(56). We have selected this testing for the following reasons: 1) it generates continuous data (time in seconds), and therefore is free of ceiling or floor effects, and 2) it has been shown to be a sensitive measure to assess improvement in speed of processing following a cognitive training intervention in older adults⁸⁴. The Timed IADL involves the timing of performance of 5 tasks that resemble everyday instrumental activities of daily living: 1) finding a telephone number for a given person in the telephone directory, 2) finding and counting out correct change from a group of coins, 3) finding and reading the ingredients on a food can label, 4) finding two food items in an array of food items on a shelf and 5) searching for and then reading the directions on a medicine container. For each task there is a 2 minute time limit, with the exception of the telephone number task which has a limit of 3 minutes. If the participant does not complete the task within the time limit, the task is terminated. The following error codes are assigned for each task: (1) completed without error and within the time limit; (2) completed with minor errors, or (3) not completed within the time limit or completed with major errors. For the tasks completed with minor errors, a time penalty is added to the completion time. This added time penalty is equal to 1 SD, based upon the data from the participants who completed the same item without error. The times for each of the tasks are transformed into Z scores which are then summed to form a composite (84). Higher scores mean worse performance.

c. Activity Monitor:

A microprocessor-linked step activity monitor (SAM) (Cyma Corporation; Mountlake Terrace,

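### Aim 3 asks whether dual-task gains translate into improved IADLs, but the only planned test is a correlation of change scores, which cannot show whether IADLs improved

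*Combined protocol and SAP*

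**What the plan says.** The Aim 3 outcomes heading sets the question: "Investigate whether improvement in DT performance translates into improved function in IADLs". The SAP restates it more narrowly as Hypothesis III: "Improvement in DT performance will be associated with improvement in IADLs function".

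The analysis under Hypothesis III takes three IADL measures (OARS IADLs, Timed IADLs, SAM) as post-test minus pre-test differences. It then says: "These measures will be correlated with DT performance measures, also represented as change scores". For OARS, "Correlations between OARS IADLs change scores and DT change scores will be calculated using non-parametric statistics, Spearman Correlation Analysis". For Timed IADLs and SAM, the correlations "will be calculated using parametric statistics: Pearson Product Moment Correlation Analysis".

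The Group by Time mixed-model ANOVA is specified for the executive-function domain scores and the ICE under Hypothesis I, and for the DT variables under Hypothesis II. The IADL measures are in neither list. The secondary analyses relate executive function to fitness. The opening paragraph of the SAP plans descriptive statistics for all variables and gives one general rule: "A two-tailed $p < 0.05$ will be considered indicative of a significant result".

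On scale direction, a higher OARS score means more disability. For Timed IADLs, "Higher scores mean worse performance". SAM is a step count.

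**The concern.** Aim 3 has two parts: DT gains go with IADL gains, and IADL function does get better. The planned correlation tests only the first. A correlation describes how participants rank or spread around their own means. It says nothing about where those means lie.

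Two errors of interpretation follow. A significant correlation in the expected direction could be reported as translation into better daily function when function was flat or falling on average. Conversely, a real improvement in IADLs that is roughly uniform across participants would leave no trace in the planned test.

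A smaller problem adds to this. The SAP does not say which sign of the correlation supports Hypothesis III for each pair, and the supporting sign differs between measures because their scales run in opposite directions.

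**Working it through.** **The plan's own figure.** There is none to reproduce. The documents give no sample size, power or effect size for Aim 3, so every n, correlation and mean change below is an assumption.

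**1. Invariance.** Let x be DT change and y be IADL change. Pearson r depends on y only through y minus its mean, and Spearman only through the ranks of y. Replacing y by y + c changes neither, so r and p are identical for every c, at any n.

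Numerical check on one simulated data set (n = 60), oriented so that positive means better:

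| Shift in IADL change | Pearson r (p) | Spearman (p) | Share of participants improving |
|---|---|---|---|
| -1 SD | 0.212 (0.105) | 0.190 (0.145) | 8% |
| 0 | 0.212 (0.105) | 0.190 (0.145) | 45% |
| +1 SD | 0.212 (0.105) | 0.190 (0.145) | 88% |

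**2. Chance of a significant result.** Assume a true correlation of 0.4. Fisher's approximation to the power is Φ(atanh(0.4) × √(n − 3) − 1.96), with atanh(0.4) = 0.4236. At n = 60 this is Φ(0.4236 × 7.550 − 1.96) = Φ(1.24) = 0.89. Mean IADL change does not enter the formula. The last three columns are from 4,000 simulated trials per cell:

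| n | Formula | Mean IADL change -1 SD | 0 | +1 SD |
|---|---|---|---|---|
| 30 | 0.60 | 0.61 | 0.61 | 0.62 |
| 60 | 0.89 | 0.90 | 0.90 | 0.90 |
| 90 | 0.98 | 0.98 | 0.98 | 0.98 |
| 120 | 0.996 | 0.996 | 0.994 | 0.996 |

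**3. The converse.** Assume both outcomes improve by 0.5 SD, with zero correlation and n = 60. The planned correlation is significant in about 5% of runs. A simple test of mean IADL change is significant in about 97%.

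**4. Sign and scaling, from the text.**
- IADL change is post minus pre. No subtraction order is given for DT change, and the secondary analyses use pre minus post.
- If DT change is also post minus pre, and faster walking counts as better, a negative correlation with OARS or Timed IADLs supports Hypothesis III, while a positive correlation with SAM does.
- Cognitive Cost and Gait Cost have no formula or direction in the documents.
- Timed IADL times become Z scores, but the reference distribution is not stated. If each visit were standardised to its own mean, mean change would be zero by construction, and even the descriptive statistics could not show improvement.

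**The case against.** The strongest reply is that the correlation does what Hypothesis III asks. The hypothesis speaks of association, and correlating change scores is a direct test of association. In a progressive disease, less decline among those with larger DT gains could be a real and useful finding. This stands, and it is why the correlations should stay. The shortfall is against the wording of Aim 3, which speaks of improved function.

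The plan also does not ignore mean IADL change altogether. It would appear in the descriptive statistics, though without a test. That stands too.

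A reader might infer that the two-tailed rule lets a wrong-direction correlation count in favour of the hypothesis. The documents do not support that. Any two-tailed test can be significant in either direction, the rule defines only a significant result, and Hypothesis III is directional. Under no association the wrong-direction share is 2.5% per pair; with a true correlation of 0.4 it was at most 0.03% of simulated runs. What remains is that the supporting sign should be written down for each pair.

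A reader might also infer that the plan would declare Hypothesis III met while function worsened. The SAP contains no such decision rule. The risk lies in how a significant correlation would be interpreted.

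**Conclusion.** The point holds as a gap between Aim 3 and its analysis. The only inferential use of the IADL measures is a correlation that cannot show improvement. The invariance is exact and needs no assumption. The figures of about 90% significant results whatever the mean IADL change (correlation 0.4, n = 60), and of about 5% against 97% in the converse case, are illustrations under assumed inputs.

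It would go too far to say that the correlation is the wrong test of Hypothesis III, or that two-tailed testing is a flaw here. This is an inexpensive improvement that changes what Aim 3 can conclude.

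**What to change.** 1. Keep the Spearman and Pearson correlations as the test of association.
2. Add the Hypothesis I Group by Time analysis for Timed IADLs, SAM and OARS IADLs. Use a rank-based or ordinal version for OARS, because the SAP itself treats it as rank-ordered.
3. Standardise Timed IADL scores at both visits to one fixed reference, such as the baseline mean and SD.
4. Orient every change score so that positive means improvement, and define the direction of the two cost measures.
5. State that DT gains will be said to translate into improved IADL function only if the correlation is significant in the hypothesised direction and the IADL measure itself improves significantly.

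One tempting alternative should be avoided: regressing IADL change on DT change and accepting any positive slope together with a predicted IADL gain, at a 1 SD DT improvement, whose 95% interval excludes zero. That rule drops the test of association. With no association, mean DT change of 0.3 SD, mean IADL change of 0.3 to 0.5 SD and n = 30 to 90 (all assumed), it succeeded in roughly 19% to 49% of simulated trials. A significant correlation in the right direction occurred in about 2.5%, and the two-part rule in item 5 cannot exceed that rate for a given pair.

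The cost is SAP wording and a few extra model runs on measures already planned at both visits. The downside is a claim that is harder to meet. The change does not settle which of the DT and IADL pairs decides the question; that is a separate matter.
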